1. SPECIFIC AIMS

Overall Aim: It is critical to be able to differentiate between unipolar depression (UD) and bipolar disorder depression (BDD) both for understanding the etiology of these similar but at the same time very different illnesses as well as for determining the type of treatment (mood stabilizers alone, antidepressants alone or a combination) that is indicated. Despite phenomenological and neurobiological research for past several decades, no single clinical or biological finding is available at present that can reliably differentiate between the two illnesses. In young patients, bipolar disorder (BD) first presents itself as depression and a history of mania or hypomania is either not available or very difficult to elicit. Only with time, and usually after years of misdiagnosis and inappropriate treatment, a proportion of the young depressed subjects start suffering from episodes of overt (hypo)mania and reveal themselves to be actually suffering from BD. Therefore, it is particularly important to be able to differentiate between young UD patients at a high risk for developing BD (HRUD) and young UD patients with low risk of developing BD (LRUD). The primary investigator has been conducting functional magnetic resonance imaging (fMRI) studies for the past decade on resting state functional connectivity and task-induced activation abnormalities in BD and UD. Preliminary findings from more recent studies suggest that resting state corticoamygdalar connectivity and task-induced activation differences may be able to differentiate between BDD, UD, HRUD and LRUD subjects. This proposal will study 40 BD, 120 UD (60 HRUD and 60 LRUD) and 40 closely matched healthy controls (HC). Aims and specific hypotheses for the present proposal, based on preliminary data collected are as follows:

SPECIFIC AIM 1: To investigate resting state corticoamygdalar connectivity and activation abnormalities which are able to differentiate between young (15– 30 yrs of age) BDD, UD and HC subjects.

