Specific Aim 1: Differentiation between BDD and UD: We will conduct a one way ANOVA with the connectivity and activation measures as dependent variables to look at differences between groups (BDD and UD). The analyses will be similar to those in our previous studies^{41, 42}. The normality assumptions will be examined using the Kolmogorov-Smirnov test. Box-Cox type transformation methods will be employed if the normality assumption is violated for the outcome variable. To adjust for multiple comparisons accounting for multiple brain ROIs and ad-hoc comparisons conducted within an ANOVA model, Bonferroni adjustment will be used to control overall type I error rates (over-all significance level will be set to 0.05). A post ANOVA logistic regression based classification model will be constructed to build a classifier between BDD and UD. Specificity and sensitivity will be examined using receiver operating characteristics (ROC) curves. We will use leave-one out cross validation method to assess predictive performance of our classification model⁹⁶.

Specific Aim 2: Differentiation between BDD, HRUD, LRUD and healthy control: We will use corticoamygdalar connectivity, amygdalar-LOFC connectivity and ACC Activation in Emotion to perform one-way ANOVA among all four groups. Prior to the analysis, each of these variables will be transformed (using the Box-Cox transformation) so that they will made as close to Gaussian as possible. The normality assumptions will be examined using the Kolmogorov-Smirnov test. Specificity and sensitivity will be examined as in Aim 1.

Specific Aim 3: Identification of imaging measures significantly affecting the rate of conversion from UD to BD: The conversion of UD subjects into BDD is defined as the time to event phenomenon and will be modeled using Cox-proportional hazard model given by,

$$\log(h(t)) = h_0(t) + \beta_1 X_1 + \beta_2 X_2 + \dots + \beta_p X_p$$

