Specific Aim 1: We used our pilot data for Left LOFC-amygdala connectivity measure. This data yielded an effect size of 0.27 for difference between BDD and UD group. 40 samples in the BDD and 120 samples in UD group will give us more than 80% power to detect an effect size as low as 0.15 for the difference in Left LOFC-amygdala connectivity between two groups. Probability of type 1 error (alpha) was set always at 0.05. For ACC-left amygdalar connectivity measure, the effect size is 0.482. With previous mentioned sample size for each group we will have 90% power to detect an effect size as low as 0.3. Similar conclusion can be made for ACC activation in NoGo-Go task for which the data yielded an effect size of 0.726 for difference between BDD and UD group. Our proposed sample size is enough to detect the difference of effects with a power close to 90% at a significance level of 0.05. Even with 20% attrition rate (i.e. 32 BDD and 96 MDD) this sample size is large enough to ensure 80% power at alpha 0.05.

Specific Aim 2: For comparisons among BDD, HRUD, LRUD and healthy subjects all three connectivity and activation measures produce power more than 80% for 40 subject per group to detect a significant difference. In the present case with 40 BDD, 60HRUD and 60 LRUD samples the power calculation is little involved, nevertheless increased sample size ensures more than 80% power at alpha= 0.05. To compare HRUD vs. LRUD left LOFC-amygdala connectivity measure yields an effect size of -0.254. For 60 subjects/group this produces 88% power at alpha 0.05.

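### The power claimed for an effect of 0.15 in left LOFC-amygdala connectivity contradicts the plan's own 88% for 0.254; on that figure it is about 46%, not over 80%

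*Combined protocol and SAP*

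**What the plan says.** Section 2c(ii)Ib, Specific Aim 1, takes a pilot effect size of 0.27 for BDD versus UD on left LOFC-amygdala connectivity. It states that 40 and 120 subjects "will give us more than 80% power to detect an effect size as low as 0.15". For ACC-amygdala connectivity at the same sample sizes it states that "we will have 90% power to detect an effect size as low as 0.3". It adds that 80% power survives 20% attrition (32 and 96).

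Under Specific Aim 2, for HRUD versus LRUD, the "left LOFC-amygdala connectivity measure yields an effect size of -0.254", and "For 60 subjects/group this produces 88% power at alpha 0.05".

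On alpha: "Probability of type 1 error (alpha) was set always at 0.05". SAS Proc Power is named. The metric, the SD and the sidedness are not stated with these figures.

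Section 1 defines the UD group as "120 UD (60 HRUD and 60 LRUD"). The Aim 1 analysis in section 2c(ii)Ia reads: "We will conduct a one way ANOVA with the connectivity and activation measures as dependent variables". For that aim, "Bonferroni adjustment will be used to control overall type I error rates". Section 2cii expects a 10% loss of subjects at baseline.

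**The concern.** Two statements about one outcome at one alpha give the smaller effect (0.15) more than 80% power and an effect 1.7 times as large (0.254) only 88%. The total is 160 in one case and 120 in the other, but the 1:3 split of the 160 cancels the advantage for a difference in means.

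LOFC-amygdala connectivity is one of the measures in both Hypothesis 1 and Hypothesis 2. A stated floor of 0.15 tells a reader that a non-significant BDD-UD difference makes effects down to about half the pilot value (0.15/0.27 = 0.56) unlikely. If power there is nearer one half or lower, a null result supports no such statement.

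**Working it through.** **Inputs.** From section 2c(ii)Ib: alpha 0.05; 0.15 at 40/120 with power above 80%; 0.254 in absolute value at 60/60 with 88%; 0.3 at 40/120 with 90%; pilot LOFC effect 0.27. Sidedness is not given, so both are shown. Power is from the noncentral t with noncentrality (effect/SD)·√m, where m = n1·n2/(n1+n2).

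**1. Information in the two designs.** 40·120/160 = 30 and 60·60/120 = 30.

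**2. Take the 88% as right.** Solving 88% at 0.254 with 60/60 gives SD 0.440 (0.491 one-sided). At that SD, 0.15 with 40/120 has noncentrality 0.15/0.440·√30 = 1.87 and power **45.8%** (50.9% one-sided).

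**3. Take 80% at 0.15 as right.** The SD must be 0.291 (0.329 one-sided). Then 0.254 at 60/60 has **99.7%** (99.5% one-sided), not 88%.

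**4. Could each contrast have its own SD?** Suppose the effects are raw differences. UD is HRUD and LRUD merged 1:1, so its SD follows from step 2: √(0.440² + (0.254/2)²) = 0.458. The pooled SD of the planned one-way ANOVA is smallest if BDD has no spread at all: √(119/158)·0.458 = 0.398. The 0.15 claim needs 0.291 or less. One-sided, the minimum is 0.440 against 0.329 needed. Simulating the pooled test for a difference of 0.15 gives:

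| BDD SD | Power, two-sided |
|---|---|
| 0 | 56% |
| 0.2 | 52% |
| 0.3 | 48% |
| 0.44 | 43% |

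**5. Other readings of effect size** (two-sided, one-sided in brackets):

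| Reading | 0.15 at 40/120 | 0.254 at 60/60 | 0.27 at 40/120 | 0.27 at 32/96 |
|---|---|---|---|---|
| d | 13% (20%) | 28% (40%) | 31% | 26% |
| f taken as d/2 | 37% (50%) | 79% (87%) | 84% | 75% |
| f from total N | 47% (60%) | 79% (87%) | 92% | 86% |
| raw, SD 0.44 (0.49 one-sided) | 46% (51%) | 88% by construction | 92% | 85% |

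If f based on total N is rescaled so that 0.254 has exactly 88%, 0.15 has 57% (61% one-sided). An f-squared reading gives over 99% for all the figures, so it cannot yield 88%, and it cannot be negative.

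**6. The plan's third figure.** The 90% at 0.3 concerns a different measure, so it is comparable only on a standardised scale. Reading f as d/2 reproduces it: 0.3 means d = 0.6, and power is 90.4%. The same reading puts 0.15 at 37%. Conversely, 80% at 0.15 would imply over 99.9% at 0.3.

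**7. Smallest d with 80% power** (two-sided 0.05): 0.515 at 40/120 and 0.516 at 60/60; 0.54 at both 36/108 and 54/54, after the 10% baseline loss. With three tests, an assumed count because the documents give none, alpha is 0.0167 and the figure at 36/108 is 0.63.

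**The case against.** The strongest reply is that the metric is unknown, so every percentage here is conditional. If the effects are Cohen's f, power follows total N and the equality of the two designs no longer applies. That is true, and the 46% belongs to the common-SD reading. But the f readings give 37% to 61% for 0.15, so the contradiction does not depend on the scale.

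A second reply is that the effects come from pilot data whose UD group need not have been a 1:1 mix, and that an unequal-variance test could reach 80% at 0.15. With the UD SD of 0.458, that takes a BDD SD of about 0.2, less than half the UD value. The documents state no such SD, and the planned analysis is a one-way ANOVA. The power statement also concerns the planned 120 UD subjects, whose composition is fixed. The preliminary-data section is not in the public text; nothing here rests on its absence, since the conflicting figures stand in one section.

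Third, the pilot effect is 0.27 and the 0.15 is only a sensitivity floor. This stands in part. If the scale is f from total N, or raw with SD 0.44, 0.27 has about 92% power and 85% to 86% after 20% attrition, so the main Aim 1 LOFC claim survives. If it is d or f = d/2, the attrition claim fails (26% or 75%). Nor is every measure in doubt: the ACC activation effect of 0.726 is adequately powered even as d (98%, and 94% at 32/96).

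Finally, the plan already tests a 20% loss for Aim 1, which is stricter than 10%. That is correct, and the 32/96 case should be kept.

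**Conclusion.** The concern holds. The two LOFC-amygdala power statements cannot both be true on a common scale, and the 0.15 floor is the one that does not fit the plan's other figures. On the plan's own 88%, power at 0.15 is 46% (51% one-sided), assuming a common SD. Letting the SDs differ raises it to at most 56% two-sided under the planned ANOVA, and the standardised readings run from 13% to about 61%. Reaching 80% would need a different test and a BDD spread that the documents do not state. Whether the pilot effect of 0.27 is adequately powered cannot be settled until the metric is known: 31% to 92% at full sample size, two-sided. All of these use unadjusted alpha 0.05, so the Bonferroni adjustment planned for Aim 1 would lower them further.

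**What to change.** - Withdraw the claim of more than 80% power at 0.15.
- State in section 2c(ii)Ib the effect-size metric, the pilot SD for each contrast, the sidedness and the number of tests.
- Recompute every Aim 1 and Aim 2 power figure on that one scale, at the alpha each analysis will use (Bonferroni-adjusted for Aim 1). Use the numbers left after the 10% baseline loss (36/108 and 54/54), and keep the 32/96 case beside them.
- Replace the 0.15 and 0.3 floors with the smallest effect detectable at 80% power.
- If an LOFC-amygdala contrast then falls below 80%, say so, report it as an estimate with a confidence interval, and do not read a non-significant result as no difference.

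The cost is recomputing and rewording the power section. The stated power becomes less favourable. No extra patients are needed.

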Adjusting for covariates: These include behavioral rating such as, attentional variables such as response time, and accuracy of response, and changes in physiological ratings; demographic variables such as age, gender, and ethnicity; scores on behavioral measures such as anxiety; treatment with concomitant medications such as atypical neuroleptics during the study; treatment history, substance abuse, and trauma history; and structural variables such as whole brain and ROI volumes. We will first identify the covariates with highly correlated with the outcome measures. Next, from this pool of highly correlated covariates to guard against multicollinearity and to conserve for degrees of freedom to ensure that we have sufficient power. To control for potential confounding effects from these covariates and not over-fit in any of our models, we will use the forward stepwise regression model building approach - so that only one covariate will be included at a time in the model - which allows us to screen out covariates that are not related to our outcome measures by using an elevated p-value ($p=0.1$) and reserve statistical power to a limited number of variables that are shown to be associated with outcome measures in our data⁹⁸.

2c(ii)lb. Sample size and power consideration: Preliminary data obtained from BDD and UD subjects were compared with healthy subjects to obtain estimates of sample size at significance level set at 0.05. Proc Power of SAS software is used to estimate the sample size.

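### The Aim 1 power figures do not agree on any one standardised effect-size scale, and the plan gives no scale, SD or sidedness

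*Combined protocol and SAP*

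**What the plan says.** Section 2c(ii)lb (Sample size and power consideration) says that pilot data were used to obtain "estimates of sample size at significance level set at 0.05", with SAS Proc Power. Under Specific Aim 1 it adds "Probability of type 1 error (alpha) was set always at 0.05" and takes "40 samples in the BDD and 120 samples in UD group".

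Three measures follow:

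- Left LOFC-amygdala connectivity: pilot effect 0.27, with more than 80% power claimed down to 0.15.
- ACC-left amygdala connectivity: "For ACC-left amygdalar connectivity measure, the effect size is 0.482", and at the stated group sizes "we will have 90% power to detect an effect size as low as 0.3".
- ACC activation in the NoGo-Go task: pilot effect 0.726, with the sample size said to be "enough to detect the difference of effects with a power close to 90% at a significance level of 0.05".

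The paragraph closes: "Even with 20% attrition rate (i.e. 32 BDD and 96 MDD) this sample size is large enough to ensure 80% power at alpha 0.05". That sentence names no measure and no effect size.

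Under Specific Aim 2 the same section reports an HRUD v LRUD effect of -0.254 for left LOFC-amygdala connectivity, with 88% power at 60 per group.

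Section 2c(ii)la plans a one-way ANOVA of BDD against UD for Aim 1. Neither section says whether an effect size is a standardised mean difference, Cohen's f or a raw difference. No SD is given, and no test is called one- or two-sided.

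**The concern.** For a comparison of two groups, an effect size is ordinarily taken as the mean difference divided by the pooled SD. On that reading, 90% power at 0.3 with 40 v 120 is far too high, and the general assurance of 80% after losing a fifth of subjects does not cover every Aim 1 measure.

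vACC-amygdala connectivity is one of the two connectivity measures in Hypothesis 1. If the standardised difference is the intended scale, that comparison has a real chance of missing an effect as large as the pilot one, and the plan says otherwise. If another scale was used, nobody can check the figures until it is named.

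**Working it through.** **Inputs.** From section 2c(ii)lb: alpha 0.05; groups 40/120 and 32/96; effects 0.15, 0.27, 0.3, 0.482 and 0.726; for Aim 2, 60/60 and -0.254. Assumed: a two-sided test, with one-sided shown as a range. No multiplicity adjustment is applied, as in the section's own figures.

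**Formula.** Two-sample t-test power from the noncentral t, with df = n1 + n2 - 2 and noncentrality d × sqrt(n1·n2/(n1 + n2)). The square root is sqrt(4800/160) = 5.477 for 40/120 and sqrt(3072/128) = 4.899 for 32/96. For two groups, Cohen's f is converted by d = 2f.

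**Trying to reproduce 90% at 0.3 (40/120).**

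- As a standardised difference: noncentrality 0.3 × 5.477 = 1.643, power 37.2% (49.7% one-sided). Not reproduced.
- As Cohen's f: d = 0.6, noncentrality 3.286, power 90.4%. Reproduced. At 32/96 the noncentrality is 2.939 and power is 83.1%, so the 80% in the attrition sentence is met too.

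**Does f fit the other figures?**

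| Effect, groups | Stated power | As standardised difference | As f (d = 2f) |
|---|---|---|---|
| 0.15, 40/120 | over 80% | 12.9% | 37.2% |
| 0.3, 40/120 | 90% | 37.2% | 90.4% |
| 0.726, 40/120 | close to 90% | 97.7% | over 99.9% |
| 0.254 in size, 60/60 | 88% | 28.1% | 78.8% |

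One-sided, f gives 87% for the Aim 2 figure, which is near 88%, but 95% at 0.3 and 50% at 0.15. Weighting f for the unequal groups (noncentrality N·f² for the F-test) gives 96.5% at 0.3 and 47% at 0.15. The 0.15 figure fails on each of these readings. Cohen's f is also non-negative by definition, so -0.254 cannot be an f.

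**Pilot effects as standardised differences, two-sided (one-sided in brackets).**

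| Measure | 40/120 | 32/96 |
|---|---|---|
| ACC-amygdala, 0.482 | 74.7% (83.7%) | 64.9% (75.9%) |
| ACC activation, 0.726 | 97.7% (99.0%) | 94.2% (97.1%) |

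Smallest detectable standardised difference, two-sided: 0.595 for 90% at 40/120, and 0.576 for 80% at 32/96.

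**Raw differences.** A raw 0.3 has 90% power at 40/120 if the SD is 0.3/0.595 = 0.50. A raw 0.726 has 90% if the SD is 0.726/0.595 = 1.22. Both are possible, because the measures differ. Within left LOFC-amygdala connectivity, 80% at 0.15 (40/120) needs an SD of at most 0.15/0.515 = 0.29, whereas 88% at 0.254 (60/60) needs about 0.254/0.577 = 0.44. Those are different group comparisons, so the SDs could differ. The plan gives none to check against.

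**The case against.** The strongest reply is that the scale is the reviewer's assumption. The planned test is an ANOVA, for which Cohen's f is a usual scale, and f = 0.3 returns both contested numbers: 90.4%, then 83.1% after attrition. Raw differences with a separate SD per measure would also satisfy both ACC sentences. With the SD of 0.50 implied above, the pilot 0.482 would be about 0.96 SD and have over 99% power even at 32/96. The attrition sentence follows the ACC activation sentences directly and names no measure, and for ACC activation it holds even as a standardised difference (94%). Finally, 20% is harsher than the 10% baseline loss expected under Methods and Design. At 36/108 the ACC-amygdala power would be 70% rather than 65%.

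Much of this stands. A reader might infer that the plan is proven wrong for ACC-amygdala connectivity, that its true power is 75% falling to 65%, or that no scale at all fits the two ACC sentences. The documents do not support any of these: the scale is never stated, raw differences fit both sentences, and the ACC activation sentence does not say that its power was computed at 0.726. The attrition sentence is also not tied to ACC-amygdala connectivity.

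The reply does not make the section consistent. f matches the 0.3 sentence but fails at 0.15 in the same paragraph and cannot be negative. Raw differences remain possible only because the SDs that would test them are absent.

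**Conclusion.** The concern holds in a limited form: the stated powers cannot all be right on any one standardised effect-size scale, and the section lacks the scale, SD and sidedness needed to settle which are right. This is more than missing detail, because each standardised reading contradicts at least one printed figure.

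The size depends on the scale. If it is the standardised difference, tested two-sided at 0.05, the 90% at 0.3 is 37%, and ACC-amygdala connectivity has 75% at its pilot effect and 65% after 20% attrition. The unrestricted 80% assurance then holds for ACC activation but not for ACC-amygdala connectivity. One-sided testing leaves both shortfalls in place (50% at 0.3; 76% at 0.482 with 32/96). If the scale is f, the two contested statements stand and the 0.15 and Aim 2 figures need correcting. If the effects are raw differences, no conclusion is possible without the SDs.

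The Bonferroni adjustment planned in section 2c(ii)la is not in any of these figures and would lower them all.

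**What to change.** In section 2c(ii)lb, state for each measure the effect-size scale, the pilot SD and whether the test is one- or two-sided. Recompute every Aim 1 figure, and the Aim 2 HRUD v LRUD figure, on that one scale. Say which measure and which effect the attrition sentence covers.

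If the scale is the standardised difference, restate as follows (two-sided 0.05):

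- ACC-amygdala connectivity: 75% power at the pilot effect 0.482; 90% needs 0.595.
- ACC activation: 98% power at 0.726.
- After 20% attrition (32 v 96): 65% and 94% respectively; 80% needs 0.58.

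Keep the sample size. The change is wording in the power section only. Its cost is that some stated figures become less favourable.

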Visit 3 will be one week following visit two and consist of mood questionnaires, Columbia Suicide Severity Rating Scale (CSSRS), Beck Scale for Suicide Ideation (BSSI), TESES (Treatment Emergent Side Effects Scale), and recording of vital signs and weight.

Visits 4 and 5 will be two weeks apart and consist of mood questionnaires, Columbia Suicide Severity Rating Scale (CSSRS), Beck Scale for Suicide Ideation (BSSI), TESES (Treatment Emergent Side Effects Scale), and recording of vital signs and weight.

Visit 6 through 10 will be one month apart and consist of mood questionnaires, Columbia Suicide Severity Rating Scale (CSSRS), Beck Scale for Suicide Ideation (BSSI), TESES (Treatment Emergent Side Effects Scale), and recording of vital signs and weight.

Visit 11 through 16 will be three months apart and consist of mood questionnaires, Columbia Suicide Severity Rating Scale (CSSRS), Beck Scale for Suicide Ideation (BSSI), TESES (Treatment Emergent Side Effects Scale), and recording of vital signs and weight.

BDD, Healthy control subjects, and UD subjects that discontinue medication treatment who opt for follow up (and sign the appropriate consent) will complete the following study procedures:

Phone assessments 1 through 8 will be three months apart and consist of mood questionnaires, and CSSRS/BSSI. These phone calls will take approximately 30 minutes. If subjects report significant mood changes they may be asked to come to the clinic for assessment. Assessment will be done with mood ratings done at V1 and V2.

Genetic Analysis:

A trained phlebotomist will collect the blood sample. Deoxyribonucleic Acid (DNA) is isolated from 10ml of blood using an organic procedure (Madisen et al.1987). The concentration and quality of DNA is determined using absorbance measurements at 260 and 280nm. The serotonin transporter (SLC6A4) proximal 5' regulatory polymorphism will be genotyped by DNA amplification following the protocol of Heils et al. (Heils et al. 1996). The primers stpr5; 5'-GGCGTTGCCGCTCTGAATTGC- 3' and stpr3; 5'-GAGGGACTGAGCTGGACAACCCAC-3' generate 484 and/or 528 base pair products. The amplification reactions are electrophoresed through 3% agarose and visualized by ethidium bromide staining using a UV transilluminator.

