Questionnaires and Tools	Screening	Basel ine	Wk 2	Wk 4	2 mon	3 mon	Every mon from 4 - 6 months	Every 3 Months from 6 months – 24 Months
Diagnostic Instrument for Genetic Studies	X							
Kiddie Schedule for Affective Disorders and Schizophrenia								
DIGS/KSADS Mood Disorders Section	X							
SCID II	X							
Visual Analog Scale	X							
MINI International Neuropsychiatric Interview (MINI)	X	X	X	X	X	X	X	X
Childhood Events and Life Events Scales	X							
Physical Examination	X							
Clinical Psychiatric Interview	X							
Family Interview for Genetic Studies (FIGS) ⁸²	X							
Laboratory Tests:	X							
fMRI SCAN		X						
Genetic blood draw	X							
S100B , antibody, and cytokine testing	X							
Antidepressant Treatment		X	X	X	X	X	X	X
Hypomania Syndrome Checklist of schedule for Affective Disorders and Schizophrenia (HSC-SADS)	X	X	X	X	X	X	X	X
17-Item Hamilton Depression Scale (HDRS) ⁷⁹ - Children’s Depression Rating Scale (CDRS-R) Hamilton Anxiety Scale (HAM-A) Screen for Child Anxiety Related Disorders (Scared)	X	X	X	X	X	X	X	X
Montgomery-Asberg Depression Scale (MADRS)	X	X	X	X	X	X	X	X
Young Mania Rating Scale (YMRS) ⁷⁷	X	X	X	X	X	X	X	X

Columbia Suicide Severity Rating Scale (CSSRS)	X	X	X	X	X	X	X	X
Beck Scale for Suicide Ideation (BSSI)	X	X	X	X	X	X	X	X
Treatment Emergent Side Effects Scale (TESES)			X	X	X	X	X	X
Clinical Global Impression Scale – for Bipolar Disorder (CGI-BP) ⁸³	X	X	X	X	X	X	X	X

III. Rating for any episodes of subthreshold or over threshold (hypo)manic symptoms: At each follow-up time point the subject will be asked for any sustained periods since the last visit in which they felt more high, irritable or energetic than their normal self³. If the patient answers in the affirmative then they would be rated on the YMRS and MSC-SADS for that period as well as for DSM-IV criteria for conversion to BD.

2c(ii)H. fMRI Scan methodology: Subjects will be imaged using state-of-the-art whole-body 3T Siemens Trio-Tim MRI scanner. Before the imaging session, subjects will be trained regarding experimental procedures. The imaging session duration will be approximately 90 minutes.

Figure 7. Imaging session:

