Specific Aim 3: Using a conservative assessment of a 6% conversion rate for the LRUD group and 14% conversion rate for HRUD group, we calculate that with a sample size of 60 per group (HRUD and LRUD) we will have 80% power with type I error fixed at 0.05, under the assumption of 20% attrition rate in both groups, to detect statistically significant imaging measures as well as differential rate of conversion. We have used Bacsafra's⁹⁶ web based program to arrive at this power calculation. For sample size requirement to differentiate between HRUD and LRUD subjects via MSC-SAD and YMRS score peak-change and slope of change we will compare the mean baseline score and the mean peak scores using two sample t-test. Peak value for each group are extrapolated from usual values seen for YMRS iduring hypomania. Under the assumption of homogeneity among groups, for both the scales a sample of size 60 will be adequate even after adjusting for 20% attrition is adequate to ensure 90% power at alpha 0.05.

[figure not shown]

Fig. 8. Hypothetical YMRS peak score changes for HRUD and LRUD group over time

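### The Aim 3 sample-size text sets out to separate HRUD from LRUD on peak change, but the test it names compares baseline with peak, so its wording and its 90% power claim need restating

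*Combined protocol and SAP*

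**What the plan says.** The text is in section 2c(ii)lb (Sample size and power consideration), Specific Aim 3.

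- **Purpose:** "For sample size requirement to differentiate between HRUD and LRUD subjects via MSC-SAD and YMRS score peak-change and slope of change".
- **Test named in the same sentence:** "we will compare the mean baseline score and the mean peak scores using two sample t-test".
- **Source of the peak values:** "Peak value for each group are extrapolated from usual values seen for YMRS iduring hypomania". The readable text gives no mean, difference or SD. Fig. 8, captioned as hypothetical peak changes in the two groups, is not reproduced in the copy reviewed.
- **Power claim:** "a sample of size 60 will be adequate even after adjusting for 20% attrition is adequate to ensure 90% power at alpha 0.05". The same paragraph sets 60 per group for HRUD and LRUD.

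Three other places bear on this:

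- Section 2c(ii)la (Statistical Analysis), Specific Aim 3, compares LRUD with HRUD by a mixed-effects model of the repeated scores, with a likelihood ratio test. It does not mention peak change.
- Exploratory Aim 3 and Exploratory Hypothesis 3 use peak change as a quantity to be correlated with baseline imaging.
- Section 2c(ii)G, part III, has subjects asked at each follow-up about any sustained elevated period since the last visit. If there was one, that period is rated on both scales.

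**The concern.** The stated purpose is a contrast between two groups of people, but the two quantities named in the test are two scores on the same people. Three problems follow if the sentence is carried out as written.

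1. **No group term.** A significant result would say nothing about HRUD against LRUD.
2. **Dependence ignored.** Baseline and peak are paired within subject, and a two-sample test treats them as independent.
3. **A maximum against a single value.** The highest of many ratings lies above one rating even when nothing changes, so the null hypothesis of equal means is false by construction.

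This is the only place where the plan attaches a group test to peak change. An analyst following it could report a rise in mania scores that comes from taking a maximum. The 90% power claim is also uninterpretable until the comparison is fixed.

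**Working it through.** **Inputs**

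- Subjects: 60 per group less 20% attrition = 60 × 0.80 = 48.
- Ratings feeding the peak: Table 3 gives weeks 2 and 4, months 2, 3, 4, 5 and 6, then "Every 3 Months from 6 months – 24 Months" (months 9, 12, 15, 18, 21, 24), which is 13. The visit list in 2c(ii)E, visits 3 to 16, gives 14.
- Alpha 0.05, taken as two-sided because the text does not say.
- Assumed, because the documents do not give them: within-person correlation ρ from 0.3 to 0.9, exchangeable ratings, and three score shapes (normal; floored integers; mostly zero).

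**Step 1: the plan's own figure.** The 90% cannot be reproduced, since the readable text has no difference or SD. It can be neither confirmed nor refuted. Working backwards for a two-group comparison:

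d = (1.960 + 1.282) × √(2/n)

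- n = 48: 3.242 × 0.204 = 0.66 (0.67 with the t distribution)
- n = 60: 3.242 × 0.183 = 0.59 (0.60 with the t distribution)

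**Step 2: how far the peak exceeds baseline with no change.** For normal scores with SD 1, the expected gap is √(1 − ρ) × E[maximum of K independent standard normals]. For K = 13 that expectation is 1.67.

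- ρ = 0.3: 0.837 × 1.67 = 1.40 SD
- ρ = 0.9: 0.316 × 1.67 = 0.53 SD

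**Step 3: rejection rate of the literal test.** The two-sample standard error is about √(2/48) = 0.204 SD. Even the smallest gap above gives t of about 0.53/0.204 = 2.6. Simulated rejection with no true change (48 subjects, 13 ratings, 4,000 trials per setting):

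| Scores | ρ = 0.3 | 0.5 | 0.7 | 0.9 |
|---|---|---|---|---|
| Normal | 100% | 100% | 100% | 98% |
| Floored integers | 100% | 100% | 99.95% | 67% |
| Mostly zero | 99.8% | 98% | 83% | 20% |

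Ignoring the pairing works against this inflation: when ρ is high, the independent-samples standard error is too large. With only 3 ratings and ρ = 0.9 the literal test rejects in under 5% of trials (2.7% with normal scores). The excess comes from taking a maximum over many ratings.

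**Step 4: the group reading on the same data.** A two-sample t-test of peak minus baseline, HRUD against LRUD, with equal follow-up rejects in 4.1% to 5.3% of trials in every 13-rating setting, which is nominal.

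**Step 5: unequal numbers of ratings.** UD subjects who stop medication and opt for follow-up move to phone contact: "Phone assessments 1 through 8 will be three months apart". With normal scores, the expected peak from 14 ratings exceeds that from 8 by √(1 − ρ) × (1.70 − 1.42). This is 0.23 SD at ρ = 0.3 and 0.125 SD at ρ = 0.8. That is a gap between follow-up paths. The gap between groups is this value times the difference in the share of subjects who switch, taken here as switching at the outset. Assumed shares:

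- 10% against 30%: 0.20 × (0.125 to 0.23) = 0.03 to 0.05 SD
- 10% against 40%: 0.30 × (0.125 to 0.23) = 0.04 to 0.07 SD

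In simulations of such splits the group test rejected in about 5% to 7% of trials.

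**The case against.** The strongest reply is that this is loose wording in a sample-size paragraph. The sentence opens with the aim of separating HRUD from LRUD, the next refers to peak values for each group, the Fig. 8 caption names both groups, and a two-sample test suits two groups. Read that way, the test holds its level. The stated HRUD-LRUD analysis of the scores is the mixed model, and the aim is labelled exploratory. All of this stands, and it limits the point to wording and to the power claim. It does not remove the point, because no sentence in the plan states a group test of peak change and the sentence that comes closest names a different contrast.

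A reader might infer three stronger things that the documents do not support.

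- **That the test is always significant.** Mania scores have a floor and entry requires YMRS below 10. With floored or mostly-zero scores and ρ = 0.9, the rate falls to 67% or 20%.
- **That the plan cannot compare HRUD with LRUD on mania scores.** The mixed model does so and does not share the defect.
- **That different follow-up paths bias the group comparison by 0.2-0.3 SD.** That would need one group wholly in clinic and the other wholly on phone from the start. Clinic visits late in follow-up have the same spacing as the calls ("Visit 11 through 16 will be three months apart"), so someone who stops later has already had the denser early visits. The interval ratings in 2c(ii)G, part III, further weaken the dependence on visit count.

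**Conclusion.** The point holds as a mismatch between stated purpose and named test. Taken literally, the baseline-against-peak comparison answers no HRUD-LRUD question and rejects in 98-100% of no-change trials with normal scores, and in 20-100% with floored or mostly-zero scores, against 5%. These figures rest on 48 subjects, 13 ratings, exchangeable scores and assumed correlations of 0.3 to 0.9. The probable intended comparison, peak minus baseline between groups, is sound at about 5% with equal follow-up, and plausible differences in follow-up path move it little. The 90% power is unverifiable from the readable text. For the between-group comparison with 48 per group it requires a standardised difference of about 0.66. The mixed model and the imaging correlations are outside this criticism.

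**What to change.** 1. **Replace the test sentence** in 2c(ii)lb, and carry it into 2c(ii)la: compare HRUD with LRUD on peak minus baseline, for YMRS and MSC-SADS separately. Include baseline score as a covariate, or as a sensitivity analysis, because the groups are not randomised.
2. **Define the peak** as the highest of all follow-up ratings, including the interval-rated elevated periods of 2c(ii)G, part III, and the conversion episode.
3. **Restate the 90% power** for this comparison with the assumed difference and SD for each scale, n per group after attrition, and sidedness.
4. **Report number of ratings and follow-up time by group** as a check. Do not restrict the peak to quarterly points. Sections 2c(ii)F and E2b6 end participation at (hypo)mania, so an early converter's episode could be lost. Adjusting for number of ratings or time at risk is not a good substitute, since the outcome itself cuts follow-up short.

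The cost is wording only, with no new visits or data. The downside is that the restated power may be lower than 90% if the assumed difference is below about 0.66 SD.
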